8.1. Primary Immunogenicity Analysis

This protocol does not define any primary immunogenicity objectives or outcome measures.

8.2. Secondary Immunogenicity Analyses

All secondary immunogenicity outcome measures will be summarized as described above.

8.3. Exploratory Immunogenicity Analyses

Completion of exploratory immunogenicity assays are contingent upon seeing scientifically relevant increased response in the M2SR-vaccinated group for the indicated assay, as determined by the scientific lead (SL) and principal investigator (PI) at the time of primary and secondary analyses.

HA ELISA reactivity with groups 1 and 2 HA stem domains of the viral hemagglutinin and serum anti-NA antibody titers to N1 and N2 neuraminidases measured by ELLA or ELISA will be completed if a scientifically relevant increase in rates of either seroconversion or 4-fold rise in either M2SR or QIV matched H3HA-specific HAI and/or MN assays in the M2SR vaccinated arm are observed after the H3N2 M2SR vaccination.

Anti-NA IgA responses to N1 and N2 neuraminidases will be assessed if a scientifically relevant increase in GMFR is observed for M2SR matched nasal sIgA is observed in the M2SR vaccinated arm after the H3N2 M2SR vaccination.

CD4⁺ and CD8⁺ T cell responses to the H3 HA present in the M2SR vaccine and pools of highly conserved Influenza A T cell epitopes will be assessed if a scientifically relevant increase in either H3 HA-specific or conserved peptide epitope-specific IFN- γ producing T cells is observed post M2SR vaccination for participants who received M2SR compared to participants who received placebo.

Planned analyses for any exploratory cellular immunology assays that are conducted based on the criteria above will be presented in an addendum to this SAP.

9. SAFETY EVALUATION

All summaries and analysis of safety data will be presented for the Safety Analysis Population. Safety summaries will be presented overall and stratified by study group. Note that solicited and unsolicited non-serious adverse events are reported following first vaccination only; as such displays are limited to first vaccination.

Listings will be sorted by study group subject ID, parameter (if applicable), and visit.

Continuous variables will be summarized using the following descriptive statistics: n (non-missing sample size), mean, standard deviation, median, maximum and minimum. All categorical measures will be summarized by the frequency and percentages (based on the non-missing sample size) of observed levels.

9.1. Demographic and Other Baseline Characteristics

Summaries of age, sex, ethnicity, and race will be presented by treatment group overall and by group for all enrolled subjects (Table 17 and Table 18). Ethnicity is categorized as Hispanic or Latino, or not Hispanic and not Latino. In accordance with NIH reporting policy, subjects may self-designate as belonging to more than one race or may refuse to identify a race, the latter reflected in the CRF as “No” to each racial option.

Individual subject listings will be presented for all demographics (Listing 6); pre-existing medical conditions (Listing 7); and concomitant medications (Listing 17).

9.1.1. Prior and Concurrent Medical Conditions

All current illnesses and past pre-existing medical conditions will be MedDRA[®] coded using MedDRA dictionary version 21.1 or higher.

Summaries of all enrolled subjects’ pre-existing medical conditions will be presented by study group (Table 19).

Individual subject listings will be presented for all medical conditions (Listing 8).

9.1.2. Prior and Concomitant Medications

Summaries of medications that were started prior to dosing and continuing at the time of dosing will be presented by WHO Drug Terms 2 and 3 and study arm for subjects in the safety population (Table 68).

Individual subject listings will be presented for all concomitant medications (Listing 17).

9.2. Measurements of Treatment Compliance

The number of doses of study product administered to subjects will be presented by study group as part of the subject disposition table (Table 12).

Table 14 and Table 15 present the number of subjects who received first and second dose, respectively, by study arm.

9.3. Adverse Events

A summary of all adverse events is provided in Table 38. A summary of those events that occurred in $\geq 5\%$ of subjects in any study group is provided in Table 39.

9.3.1. Solicited Events and Symptoms

Systemic and upper respiratory (local) solicited adverse events were collected pre-vaccination, and systemic and local solicited adverse events were collected 30 minutes post-vaccination and then daily for 7 days after first vaccination and graded on a scale of 0 (absent), 1 (mild), 2 (moderate) and 3 (severe). Systemic events include: fever, feverishness (chills/shivering/sweating), fatigue (tiredness), malaise (general unwell feeling), myalgia (body aches/muscular pain), arthralgia (joint pain), headache, flushing, decreased activity, decreased appetite, abdominal pain, nausea, vomiting, diarrhea, eye pruritus, eye redness (conjunctivitis), and allergy. Local events include: runny nose, stuffy nose/congestion, sneezing, nasal pain/irritation, nasal bleeding/epistaxis, sinus pressure/pain, sore throat/sore/scratchy/itchy or painful throat, cough, trouble breathing/shortness of breath. Wheezing experienced on or before Day 8 is considered a solicited event. The grading scales for solicited systemic and local (upper respiratory) adverse events are provided in [Table 7](#) and [Table 6](#), respectively. Grading for wheezing events is provided in [Table 9](#).

The proportion of subjects reporting at least one solicited adverse event will be summarized for each solicited adverse event, any systemic symptom, any local symptom, and any symptoms. The 95% CI calculated using Blaker methodology from a binomial distribution (SAS Proc Freq with a binomial option) will be presented ([Table 40](#)).

For each systemic and local event, any systemic event, any local event, and any solicited event, the maximum severity over 7 days after first vaccination will be summarized for the Safety population. The number and percentage of subjects reporting each event will be summarized by the maximum severity and study group. For each event the denominator is the number of subjects with non-missing data for the specific event ([Table 42](#)).

The number of subjects reporting a solicited adverse event will be summarized for each day post vaccination in a summary table ([Table 43](#) and [Table 44](#)) and graphically in a bar chart ([Figure 50](#) and [Figure 51](#)). The difference proportion of subjects experiencing any individual symptom, any local or systemic symptom, and any symptom overall will be presented in [Table 41](#).

Solicited adverse events by subject will be presented in [Listing 11](#) and [Listing 12](#).

9.3.2. Unsolicited Adverse Events

When calculating the incidence of unsolicited AEs (i.e., on a per subject basis), each subject will only be counted once at the highest severity and/or relationship, and any repetitions of AEs within a subject will be ignored; the denominator will be the total number of subjects in the safety population. All AEs reported will be included in the summaries and analyses.

The number and percentage of subjects reporting at least one unsolicited AE will be summarized by MedDRA system organ class and preferred term. Denominators for percentages are the number of subjects who received the study vaccination summarized. A 95% CI will be presented for the percentage of subjects reporting any unsolicited AE (serious or non-serious) for each MedDRA system organ class and preferred term

A listing of all reported AEs by subject will be presented in [Listing 13](#), sorted by study group, subject ID, and AE Number.

The following summaries for unsolicited adverse events will be presented by MedDRA system organ class, preferred term, vaccination and study group:

- Subject incidence and total frequency of adverse events over time with 95% CI (Days 1-8, Days > 8) (Table 45);
- Summary of severity and relationship to study product (Table 46);
- Subject incidence and total frequency of related adverse events over time (Days 1-8, Days > 8) (Table 47);
- Subject listing of non-serious adverse events of moderate or greater severity (Table 49);
- Bar charts of the frequency and incidence of non-serious adverse events by severity and MedDRA system organ class (Figure 52 and Figure 53);
- Bar charts of non-serious adverse events by relationship (Figure 54 and Figure 55).

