3.2. Endpoints

3.2.1. Primary

Safety:

- Frequency of solicited upper respiratory and systemic reactogenicity through approximately Day 8 after the first study vaccination.
- Frequency of unsolicited non-serious adverse events from the time of study vaccination through 21 days after the first study vaccination.
- Frequency of SAEs, regardless of seriousness or relationship to study vaccination, from receipt of the first vaccination throughout the entire study.
- Frequency of New Onset Chronic Medical Conditions (NOCMC) and AESIs that develop from receipt of vaccination through 3 months after first study vaccination.

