14.3.1.2 Unsolicited Adverse Events

Table 45: Summary of Unsolicited Adverse Events by Study Group, MedDRA System Organ Class and Preferred Term – Safety Population

[Implementation Note: SOC and PT will be sorted by number of subjects. Any SOC that is in either group should be presented (i.e. if SOC1 has 1 event in M2SR but 0 in placebo, SOC1 will still be shown for placebo). For any SOC with a single PT the “Any PT” row will be omitted.]

Study Arm	MedDRA System Organ Class	MedDRA Preferred Term	Day 1-7 Post Vaccination (N=X)				Day 8-21 Post Vaccination (N=X)				Any Time Post Vaccination (N=X)			
			n	%	95% CI	Events	n	%	95% CI	Events	n	%	95% CI	Events
M2SR (N=X)	Any SOC	Any PT	x	xx	xx, xx	x	x	xx	xx, xx	x	x	xx	xx, xx	x
	[SOC 1]	Any PT												
		[PT 1]												
		[PT 2]												
	[SOC 2]	Any PT												
		[PT 1]												
		[PT 2]												
Placebo (N=X)	Any SOC	Any PT	x	xx	xx, xx	x	x	xx	xx, xx	x	x	xx	xx, xx	x
	[SOC 1]	Any PT												
		[PT 1]												
		[PT 2]												
	[SOC 2]	Any PT												
		[PT 1]												
		[PT 2]												

Note: N = number of subjects in the Safety Population. This table presents number and percentage of subjects. A subject is only counted once per PT/time point.

Table 46: Unsolicited Adverse Events by MedDRA System Organ Class and Preferred Term, Maximum Severity, Relationship, and Study Group – Safety Population

[Implementation Note: SOC and PT will be sorted by the total number of subjects (any severity, any relationship, descending).]

MedDRA System Organ Class	Preferred Term	Severity	M2SR (N = X)						Placebo (N = X)						All Subjects (N = X)							
			Related		Not Related		Total		Related		Not Related		Total		Related		Not Related		Total			
			n	%	n	%	n	%	n	%	n	%	n	%	n	%	n	%	n	%		
Any SOC	Any PT	Any Severity	x	xx	x	xx	x	xx	x	xx	x	xx	x	xx	x	xx	x	xx	x	xx	x	xx
		Mild	x	xx	x	xx	x	xx	x	xx	x	xx	x	xx	x	xx	x	xx	x	xx	x	xx
		Moderate	x	xx	x	xx	x	xx	x	xx	x	xx	x	xx	x	xx	x	xx	x	xx	x	xx
		Severe	x	xx	x	xx	x	xx	x	xx	x	xx	x	xx	x	xx	x	xx	x	xx	x	xx
SOC 1	PT 1	Any Severity	x	xx	x	xx	x	xx	x	xx	x	xx	x	xx	x	xx	x	xx	x	xx	x	xx
		Mild	x	xx	x	xx	x	xx	x	xx	x	xx	x	xx	x	xx	x	xx	x	xx	x	xx
		Moderate	x	xx	x	xx	x	xx	x	xx	x	xx	x	xx	x	xx	x	xx	x	xx	x	xx
		Severe	x	xx	x	xx	x	xx	x	xx	x	xx	x	xx	x	xx	x	xx	x	xx	x	xx
	PT 2	Any Severity	x	xx	x	xx	x	xx	x	xx	x	xx	x	xx	x	xx	x	xx	x	xx	x	xx
		Mild	x	xx	x	xx	x	xx	x	xx	x	xx	x	xx	x	xx	x	xx	x	xx	x	xx
		Moderate	x	xx	x	xx	x	xx	x	xx	x	xx	x	xx	x	xx	x	xx	x	xx	x	xx

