Adverse Event	Associated with Vac No.	No. of Days Post Associated Vaccination (Duration)	Severity	SAE? AESI? NOCMC?	Relationship to Study Treatment	In Not Related, Alternative Etiology	Action Taken with Study Treatment	Subject Discontinued Due to AE	Outcome	MedDRA System Organ Class	MedDRA Preferred Term
Study Group: , Subject ID: , AE Number:											
Comments:											
Study Group: , Subject ID: , AE Number:											
Comments:											
Note: For additional details about SAEs, see Table: xx.											

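### No planned display gives the second primary safety endpoint: subjects per arm with a non-serious unsolicited AE through 21 days after dose 1, with a confidence interval

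*SAP*

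**What the plan says.** SAP 3.2.1 repeats the endpoint in Protocol 3.2.1: "Frequency of unsolicited non-serious adverse events from the time of study vaccination through 21 days after the first study vaccination". It carries two limits: non-serious events only, and 21 days.

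Neither limit appears in the analysis text. SAP 9.3.2 says: "A 95% CI will be presented for the percentage of subjects reporting any unsolicited AE (serious or non-serious"), for each system organ class and preferred term. It also says: "All AEs reported will be included in the summaries and analyses".

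For time windows, the 9.3.2 text plans "Subject incidence and total frequency of adverse events over time with 95% CI (Days 1-8, Days > 8) (Table 45"). The shells of Tables 45 and 47 instead have a Day 1-7 column, a column headed "Day 8-21 Post Vaccination (N=X"), and one headed "Any Time Post Vaccination".

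Three other places bear on the point:

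- SAP 4.5.2 sets different collection periods: non-serious AEs to about 21 days after dose 1, AESIs and NOCMCs to 3 months, and SAEs to 12 months.
- Listing 13, the listing of unsolicited AEs, has a column that flags "SAE? AESI? NOCMC", so these events are held among the unsolicited AEs.
- The opening of SAP 9 limits displays to the first vaccination, because solicited and non-serious unsolicited events are reported only then.

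**The concern.** Safety is the only primary objective, and this is one of its four endpoints. If the shells are programmed as written, the clinical study report will contain several unsolicited-AE percentages, and none will be the one that was defined. A reader will probably take the Any SOC, Any Time row of Table 45 as the result. That row has no stated upper limit. It can therefore combine three weeks in which all AEs were captured with a later period in which only SAEs, AESIs and NOCMCs were recorded.

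**Working it through.** **The plan's own figure.** SAP Table 3 is the only stated figure that bears on unsolicited AEs: the chance of seeing at least one event, 1 - (1 - p)^n. For n = 25 it gives 92.8%, 22.2%, 2.5% and 0.25% at p = 10%, 1%, 0.1% and 0.01%, against a printed 93, 22, 3 and <1. For n = 50 it gives 99.5%, 39.5%, 4.9% and 0.5%, against >99, 40, 5 and <1. The table reproduces to within one point. The defect does not depend on it.

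**Each planned display set against the endpoint.**

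| Display | Non-serious only? | Whole 21 days as one period? | Subjects by arm? | CI? |
|---|---|---|---|---|
| Table 38, unsolicited row | No | No time limit | Yes | No |
| Table 39, non-serious block | Yes, but only terms at 5% or more of a group | No stated window | Yes | No |
| Table 45, Day 1-7 and Day 8-21 | No | No, two separate parts | Yes | Yes |
| Table 45, Any Time | No | No time limit | Yes | Yes |
| Table 46 | No | No time limit | Yes | No |
| Table 47 | No, and related events only | As Table 45 | Yes | Yes |
| Table 49 | Yes, but moderate or severe only | No stated window | Listing only | No |
| Figures 52 and 54 | Yes in the text, no in the shells | No stated window | Event counts | No |
| Figures 53 and 55 | Yes in the text, no in the shells | No stated window | Percentages | No |

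No row meets all four conditions.

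**Table 39 threshold.** With 25 per arm, 1/25 = 4.0% is below 5% and 2/25 = 8.0% is above it. With 22 per arm, 1/22 = 4.5% is still below. A term seen in only one child per arm drops out.

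**Why the two period columns cannot be added.** A child with events in both periods counts once in each. Take assumed counts of 6 of 25 in Day 1-7 and 5 of 25 in Day 8-21. The 21-day incidence then lies between max(6, 5)/25 = 24% and (6 + 5)/25 = 44%, depending on overlap. Both columns also include any SAE in the period.

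**How far an unlimited figure can move.** Let x of 25 children have a non-serious AE within 21 days, and let k others have only serious or later events. The endpoint is x/25, Any Time reads (x + k)/25, and the excess is k/25, or 4 points per child. The documents give no AE counts, so x and k below are assumptions.

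| x | k = 0 (Blaker 95% CI) | k = 1 | k = 2 | k = 3 |
|---|---|---|---|---|
| 5 | 20% (8.2-39.7) | 24% (11.0-43.8) | 28% (12.8-47.9) | 32% (16.1-52.1) |
| 8 | 32% (16.1-52.1) | 36% (19.0-56.2) | 40% (22.2-60.4) | 44% (25.1-64.5) |

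**Text against shells.** The 9.3.2 text leaves its second period open-ended, while the shells close it at Day 21. The lower boundary might be reconciled if the text counts study days and the shells count days after vaccination; the upper boundary cannot. For Figures 52-55 the text says non-serious events, while the shell notes call for all unsolicited events and all doses. The shell notes also conflict with the first-vaccination limit at the start of SAP 9.

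**The case against.** The case for leaving the plan alone has real content. Protocol 11.4.2 itself asks for exact intervals for AEs in aggregate without a seriousness split. The trial is exploratory and tests no formal hypothesis. Tables 45 and 47 do have two bounded columns with n, % and a CI by arm, and these exclude every late event; only SAEs within the window contaminate them. Any Time, beside those columns and under the first-vaccination limit, could be read as their union. Listing 13 holds the seriousness flag and the days since vaccination, so the endpoint can be derived.

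Much of this stands, and it limits the point. It does not supply the missing estimate: a primary endpoint should be tabulated, not left to be rebuilt from a listing.

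Three stronger readings are tempting but unsupported:

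- *The reported rate is inflated.* This needs at least one child whose unsolicited events are all serious or late. The documents give no such count, and Protocol 11.4.2 expects few SAEs, AESIs and NOCMCs. The 5% in that section is a trigger for tabulating and testing, not an expected rate.
- *Events are double-counted.* Showing an event in a pooled summary and again in its own listing is not double-counting, since 9.3.2 counts each subject once. A non-serious AESI or NOCMC within 21 days also belongs to this endpoint.
- *Any Time covers a full year.* SAEs, AESIs and NOCMCs after Day 22 but before the Day 92 QIV dose still follow the first vaccination. Whether SAEs after QIV enter is unclear: SAP 9 suggests not, while the rule to include all reported AEs and the Figure 52-55 notes suggest that they do.

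**Conclusion.** The point holds as a mismatch between endpoint and analysis. Followed as written, the SAP does not produce the subject-level incidence, with an interval by arm, for one of its four primary safety endpoints. That conclusion rests on the text alone and needs no assumed event rate.

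The size of any numerical discrepancy is conditional. Any Time in Tables 45 and 47, and the corresponding figures in Tables 38 and 46, may exceed the rate for the same events under the endpoint's limits by 4 points per arm for each affected child. This assumes 25 per arm, and the excess is zero if no child is affected. The plan should be corrected, but nothing here shows that the reported safety profile would mislead.

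**What to change.** 1. Add to Table 45 a column for non-serious unsolicited AEs from dose 1 through 21 days after first vaccination, with n, % and a Blaker 95% CI by arm, counting each subject once. Add the matching row to Table 38. Blaker intervals are already the SAP's method for solicited events (9.3.1).
2. State in 9.3.2 that this column is the analysis of the second primary endpoint. Keep non-serious AESIs and NOCMCs with onset within 21 days in it. Report SAEs, and later AESIs and NOCMCs, in Tables 48, 50 and 51.
3. Align the time windows in the 9.3.2 text with the shells of Tables 45 and 47.
4. Make the notes to Figures 52-55 match the text: non-serious events, after first vaccination.
5. Define Any Time, including whether SAEs after QIV count, or label it as mixed capture.

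The cost is SAP wording, one column and one row. Listing 13 already carries the seriousness flag and the days since vaccination, so no new data are needed. Table 38 is marked for the interim report, so its new row applies there too.

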9.4. Deaths, Serious Adverse Events and other Significant Adverse Events

The following listings will be presented including Subject ID, Age (years) AE Description, AE Onset Date/End Date, Last Vaccination Received/Days Post Vaccination, Reason Reported as an SAE, Relationship to Treatment, Alternate Etiology if not Related, Outcome, and Duration of Event (days):

- Deaths and Serious Adverse Events (Table 48);
- Adverse Events of Special Interest (Table 50);
- New Onset Chronic Medical Conditions (Table 51).

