#### **3.2. Study Outcome Measures**

##### **3.2.1. Primary:**

Safety:

- Frequency of solicited upper respiratory and systemic reactogenicity through approximately Day 8 after the first study vaccination.

- 
- Frequency of unsolicited non-serious adverse events from the time of study vaccination through 21 days after the first study vaccination.
  - Frequency of SAEs, regardless of seriousness or relationship to study vaccination, from receipt of the first vaccination throughout the entire study.
  - Frequency of New Onset Chronic Medical Conditions (NOCMC) and AESIs that develop from receipt of vaccination through 3 months after first study vaccination.

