#### **11.4.2. Primary Safety Data**

Summaries and analysis of safety data will be presented for the Safety Analysis Population.

Solicited AEs will be summarized by severity for each day after the first study vaccination (Days 1-8 post vaccination) and as the maximum severity over all 8 days. Additionally, solicited AEs will be analyzed by taking the most severe response over the follow-up period, dichotomizing into a binary variable (none versus mild, moderate, or severe) and using standard techniques, such as exact confidence intervals, to summarize the number and percentage of subjects reporting each symptom, any upper respiratory symptom and any systemic symptom by treatment arm.

Unsolicited AEs will be coded by Medical Dictionary for Regulatory Activities (MedDRA®) for preferred term and system organ class (SOC). The number of SAEs, AESIs, and NOCMCs is expected to be small in this trial and will be reported by detailed listing showing the event description, MedDRA preferred term and SOC, relevant dates (study vaccinations and AEs), severity, relatedness, and outcome for each event. If more than 5% of subjects report SAEs, and AESIs, and NOCMCs then the number and percentage of subjects reporting each type of event will be reported by treatment arm and compared using Fisher's Exact test. Unsolicited AEs will be summarized as number and percentage of subjects reporting at least one event in each MedDRA preferred term and SOC, cross tabulated by severity and relationship to study product. Additionally, the proportion of subjects and exact 95% confidence intervals of AEs in aggregate and by MedDRA categories will be computed.

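### The protocol's conditional Fisher's Exact comparison of SAEs, AESIs and NOCMCs is not carried into the SAP, and its removal is not recorded

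*SAP*

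**What the plan says.** These events make up two of the four primary safety outcomes: "Frequency of SAEs, regardless of seriousness or relationship to study vaccination, from receipt of the first vaccination throughout the entire study" (Protocol 3.2.1) and "Frequency of New Onset Chronic Medical Conditions (NOCMC) and AESIs that develop from receipt of vaccination through 3 months" (SAP 3.2.1).

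Protocol 11.4.2 sets a two-step rule. The default is a listing: "The number of SAEs, AESIs, and NOCMCs is expected to be small in this trial and will be reported by detailed listing". The second step is conditional and opens "If more than 5% of subjects report SAEs, and AESIs, and NOCMCs then the number and percentage of subjects reporting each type of event". Above that level, the arms are tabulated side by side and tested against each other with Fisher's Exact test.

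SAP 9.4 opens with "The following listings will be presented including Subject ID, Age (years) AE Description" and names Tables 48, 50 and 51, all of them listings. It has no 5% trigger and no comparison. Elsewhere in the SAP:

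- **Table 38** gives n and % by arm for subjects with at least one SAE, AESI or NOCMC, whatever the frequency.
- **Table 39** gives n, % and event counts by arm for terms reaching 5% in any study group, with a separate block for serious events.
- **SAP 9.3.2 and Table 45** give a 95% CI for unsolicited AEs, serious or not, by system organ class and preferred term within each arm.
- **Table 41** gives a between-arm difference with 95% CI, for solicited events only. SAP 3.3 and 9.3.1 count wheezing through Visit 02 as solicited, so it has a row there.

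Fisher's test appears nowhere in the SAP. SAP 12, which summarises changes to the planned analyses, does not mention dropping it.

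**The concern.** The two documents prescribe different analyses for the same primary safety outcomes, and neither says which governs. SAP 1 presents the SAP as describing all planned analyses. If three or more subjects report an AESI, the analyst must either depart from the protocol or add a comparison that the SAP does not specify, after seeing the data.

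The coverage is also uneven. Every solicited symptom, down to sneezing, gets an M2SR minus placebo difference with an interval. SAEs, NOCMCs, otitis media and later wheezing do not.

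A smaller drafting problem lies in the trigger. The phrase "If more than 5% of subjects report SAEs, and AESIs, and NOCMCs" does not say whether the 5% applies to each type or to the three combined.

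**Working it through.** **1. The plan's own safety figure.** The documents give no operating characteristics for this comparison. The only safety calculation is Table 3, the chance of at least one event, 1 − (1 − p)^n. For n = 25 / 50 it gives 92.8% / 99.5% at p = 10%, 22.2% / 39.5% at 1%, 2.5% / 4.9% at 0.1% and 0.25% / 0.50% at 0.01%. Table 3 prints 93 / >99, 22 / 40, 3 / 5 and <1 / <1. It reproduces to within a point (the 0.1%, n = 25 cell is 2.47, printed as 3).

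**2. The trigger.** The planned sample is 50, at 25 per arm (Protocol 11.2). More than 5% of 50 is more than 2.5, so at least 3 subjects. The chance of 3 or more of 50 is 8%, 46% and 89% at assumed overall rates of 2%, 5% and 10%.

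**3. What Fisher's test can show at 25 v 25.** The documents set no significance level for this test; two-sided 0.05 is assumed. For k v 0 the two-sided p is 2 × C(25,k) / C(50,k):

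- 3 v 0: 2 × 2,300 / 19,600 = 0.235
- 4 v 0: 0.110
- 5 v 0: 0.0502
- 6 v 0: 2 × 177,100 / 15,890,700 = 0.022

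With events in both arms, 6 v 1 gives 0.098 and 7 v 1 gives 0.049; with 2 in the lower arm, 9 are needed. So p < 0.05 needs at least 6 v 0, 7 v 1 or 9 v 2, and a count of exactly 3 cannot reach it.

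**4. Power.** This is the sum over all pairs (i, j) of Bin(i; 25, p1) × Bin(j; 25, p0) wherever Fisher p < 0.05. None of the rates comes from the documents.

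| M2SR v placebo (assumed) | Power |
|---|---|
| 10% v 2% | 2% |
| 12% v 4% | 4% |
| 15% v 5% | 7% |
| 20% v 5% | 20% |
| 24% v 4% | 38% |
| 30% v 5% | 55% |
| 40% v 5% | 82% |

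**5. What an interval adds.** A Newcombe 95% interval is used for illustration. For 3 v 0 the Wilson limits are 4.2% to 30.0% for 3/25 and 0% to 13.3% for 0/25. The difference is 12 points. Its lower limit is 12 − √[(12 − 4.2)² + 13.3²] = −3.5 and its upper limit is 12 + (30.0 − 12) = 30. For 6 v 0 the difference is 24 points (5.7 to 43.4).

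**The case against.** The strongest reply is that little is lost. The study is exploratory and tests no formal hypothesis (Protocol 11.1; SAP 6.8). The primary outcomes are frequencies, not comparisons. The protocol expects few such events and makes listings the default, which SAP 9.4 delivers. Protocol 11.4 also leaves the SAP to define the analyses for the final report. Most of this stands as a limit on the size of the problem. It does not remove the conflict, because the same exploratory protocol specifies this comparison, and SAP 6.8 uses the absence of a hypothesis only to justify making no multiplicity adjustment.

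A reader might infer that an imbalance would appear only as subject lines. The documents do not support that. Table 38 gives n and % by arm unconditionally, which is more than the protocol's conditional tabulation. Table 39 can be reached by 2 of 25 in one arm (8%). Table 45 gives within-arm intervals by term, and early wheezing is already compared in Table 41.

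A reader might also take the trigger to require all three event types to exceed 5%, so that frequent AESIs without NOCMCs would never be compared. That is only one of several readings, and the sentence goes on to refer to each type of event. The wording needs settling, but it does not establish that rule.

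Finally, the protocol asked for a test and not an effect estimate, so the difference with CI goes beyond restoring what was dropped. That is correct. It is recommended on its merits.

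**Conclusion.** The point holds as an undeclared inconsistency between protocol and SAP on primary safety outcomes. The tabulation half of the protocol's rule survives; the comparison half does not. SAEs, NOCMCs, otitis media and wheezing after Visit 02 are left with no between-arm estimate or test.

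It should not be read as the loss of a confirmatory primary test, or of a sensitive safety check. At 25 per arm the test cannot be significant at the trigger count, and its power depends entirely on assumed rates. The lower end of the range fits better with the protocol's expectation of few events. The gain is therefore consistency between the documents and, mainly, a difference with an interval, which says more than the p-value. These figures assume 25 vaccinated subjects per arm and a two-sided 0.05 level.

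**What to change.** In SAP 9.4 and Table 38:

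- Restore the Fisher's Exact comparison for any of the three types (SAE, AESI, NOCMC) reported by more than 5% of subjects, that is 3 or more of 50.
- Add the M2SR minus placebo difference with 95% CI for each type, and name the interval method.
- State that the 5% trigger applies to each type separately, and align the wording of Protocol 11.4.2 at the next amendment.
- Limit the comparison to the final analysis. Table 38 is marked for the interim report, where SAP 6.6 allows no hypothesis testing.

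SAP 6.3.3 literally restricts the Safety population to M2SR recipients. It must be read or corrected to include placebo recipients, or there is nothing to compare.

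If the sponsor prefers not to test, recording and justifying the removal in SAP 12 would resolve the inconsistency, and the difference with CI would still be worth adding.

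The cost is a few sentences and extra columns on three table rows, with no new data.
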